This pilot proposal is a randomized longitudinal single-blind sham-controlled intervention. Individuals with PSF will be randomly assigned to the sham or a-tDCS treatment group. Before and after five consecutive days of a-tDCS applied bilaterally over the left and right lower extremity motor cortex, PSF and nervous system and peripheral inflammation will be measured, similar to De Doncker et al. (2021). The tDCS treatment will consist of twenty minutes of 4 mA a-tDCS delivered via two carbon rubber electrodes placed inside sponge pads (1x1 tDCS, Soterix, USA). The current will be ramped up 4 mA over 30 seconds. Each electrode has a surface area of 70 cm², resulting in a current density of 0.06 mA/cm² and a charge density of 1.1 C/cm², which are within current safety guidelines (Bikson et al. 2016). The anode electrode will be centered on the interhemispheric fissure and the central sulcus. This area was chosen due to its previous use in fatigue studies using neuromodulation (multiple sclerosis, Ferrucci et al. 2014; fibromyalgia, Altas et al. 2019; Stroke, De Doncker et al. 2021). The motor cortex is being used more often in neuromodulation studies due to its structural and functional connectivity to cortical and subcortical networks/nodes, e.g. basal ganglia, cingulate cortex. The cathodal electrode will be placed on the nonparetic shoulder. Modeling of cephalic and extracephalic tDCS montages indicates that extracephalic placement of the cathode leads to deeper current flow in the somatosensory cortex (Noetscher et al. 2014). The sham tDCS procedure will be performed in the same manner as active a-tDCS, however, the current will be ramped up and down over 30 seconds (Fridricksson et al. 2018). Figure 2 displays the protocol timeline. Days 2-6 will be consecutive, no more than 36 hours will be allowed between treatment visits. If more than 36 hours elapses the participant will be withdrawn from the study. The measurement of state fatigue, via f-VAS, will be performed before and after each tDCS treatment visit. Follow-up assessments of state and trait fatigue will be performed via phone at one (Follow-up 1), two (Follow-up 2), and four weeks post-treatment (Follow-up 3). The primary study outcome will be the comparison of the FSS scores obtain at baseline (Visit 1) and one week post-tDCS (Follow-up 1).

Neuroimaging

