
Table 1: Clinical Outcome Measures

Domain	Instrument
Fatigue (State)	Visual Analogue Scale
Fatigue (Trait)	* Fatigue Severity Scale (FSS) (Krupp et al. 1989) Modified Fatigue Impact Scale (mFIS) (Fisk et al. 1994) Fatigue Assessment Scale (FAS) (Michielsen et al. 2003)
Anxiety	Hospital Anxiety and Depression Scale (Zigmond and Snaith 1983)
Depression	Patient Health Questionnaire 9 (PHQ-9) (Spitzer and Williams 1999)
Pain	Defense and Veterans Pain Rating Scale (DVPRS) (Polomano et al. 2016)
Physical Function / Mobility	10 m walk over GAITRite (Kindred et al. 2019)
Community Participation / Quality of Life	Standard Form 36 (Anderson et al. 1996)

* Primary outcome measure for Aim 1

Statistical Analysis

Aim 1 Hypothesis: Five days of a-tDCS applied to the lower extremity motor cortex will result in a reduction of PSF severity in individuals with chronic stroke. A two-factor, between-subjects factor of GROUP (active a-tDCS, sham) and within-subjects factor of TIMEPOINT (pre, post), mixed model ANOVA will be used to test this hypothesis. The primary outcome variable for this analysis is the FSS scores. We will also calculate measures of effect size to power future studies.

Aim 2 Hypothesis: Five days of a-tDCS applied to the lower extremity motor cortex will result in a reduction of inflammatory markers within the central nervous system and the peripheral blood. Pre- and post-intervention markers of inflammation will be compared using a mixed model, two-factor ((between-subjects factor of GROUP (active a-tDCS, sham) and within-subjects factor of TIMEPOINT (pre, post)), ANOVA. Each outcome measure (MI, tCR, IL-1, TNF- α , etc) will be tested independently.

Additional Analyses: Examine the possible relationship between PSF severity and inflammatory markers. This relationship may provide mechanistic insight into the effect of tDCS on PSF and allow us to possibly predict future responders/non-responders to a-tDCS treatments of PSF. Pearson's correlations will be calculated between baseline measures of inflammation and FSS scores to determine a possible role of current state inflammation on PSF severity. Correlations between the change in FSS scores and inflammation, pre- and post-a-tDCS, will be calculated to provide preliminary evidence of a possible mechanism of reduced inflammation and improved PSF.

Potential Problems / Solutions

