Some groups have reported a 50% response rate to tDCS. Due to our small sample, non-responders may reduce our statistical power. A post-hoc response analysis, defined as a change greater than the minimally clinically important difference of 0.45 (Nordin et al. 2016), will be performed to power future studies. Placing the ¹H-MRS voxel within the basal ganglia is a logical starting place based on the published literature. However, it is possible that inflammatory markers outside this region are as influential or more so than basal ganglia measures. Future work may be required to determine which brain regions are best to assess with ¹H-MRS. Another limitation is that only a-tDCS is being tested. Cathodal tDCS (c-tDCS) has been reported to have similar long-term effects on gene expression and protein synthesis. The benefits of tDCS on fatigue, to date, have mostly investigated a-tDCS although future investigations need to determine if c-tDCS may be a viable treatment option. Another area that will need to be addressed in future studies is if our post-intervention measurements of metabolite changes reflect the last episode of treatment or if they are indicative of long-term changes in response to tDCS. Future studies will also need to assess the optimal intervention length and follow-up periods.

Biostatistical Justification

This pilot work is based on a similar study investigating a-tDCS' effects on post-stroke fatigue (De Doncker et al. 2021). The FSS is the primary measure of fatigue severity and the minimally clinically important difference (MCID) was reported to be 0.45 (Nordin et al. 2016), with changes greater than this resulting in reported improvements in QOL. To detect this level of change with 80% power and an alpha = 0.05 between two groups using a within-between-subjects interaction ANOVA a minimum sample of 8 individuals in each group is required. We will enroll 24 participants (12 a-tDCS, 12 sham) to account for any drop-out, loss to follow-up, or complications during data collection. We have projected to perform recruitment and data collection activities over nine months.

REFERENCES

Altas, E. U., Askin, A., Besiroglu, L., & Tosun, A. (2019). Is high-frequency repetitive transcranial magnetic stimulation of the left primary motor cortex superior to the stimulation of the left dorsolateral prefrontal cortex in fibromyalgia syndrome? *Somatosens Mot Res*, 36(1), 56-62.

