The intervention being studied is a five-session anodal transcranial direct current stimulation (tDCS) intervention delivered over five consecutive days. Measures of post-stroke fatigue and inflammation (central inflammation measured by magnetic resonance spectroscopy and peripheral markers measured via blood analysis) will be made before and after the intervention.

Trial Management. The study will be primarily managed from the Functional Neurostimulation Laboratory ([name], PI) within the Division of Physical Therapy within the College of Health Professions at the Medical University of South Carolina. The target population is adults more than six months post-stroke with clinically present fatigue (average Fatigue Severity Scale > 4).

Data Management and Analysis

The primary outcome of the study is the change in post-stroke fatigue severity (fatigue severity scale (FSS), pre- and post-intervention) and markers of central (measured using magnetic resonance spectroscopy (MRS)) and peripheral (measured via blood analysis) inflammatory markers. Analyses will be guided by the specific hypotheses of the study. Post-hoc exploratory analyses will be conducted with two-tailed tests and more conservative statistical procedures which guard against Type I error (e.g., Tukey tests). All primary hypotheses will be tested at level of significance $\alpha=0.05$. We will also estimate the effect sizes of interest and provide 95% confidence intervals for them.

Quality Assurance

Data quality will be monitored by random inspection of the completed forms by research staff/PI.

Regulatory Issues. All unexpected Adverse Events (AEs) will be reported to the MUSC IRB within 10 working days. Serious AEs (SAEs) will be reported within 24-business hours. Follow-up of all unexpected and serious AEs will also be reported to the IRB. All AEs will be reviewed weekly by the PI and yearly by the IRB. Any significant actions taken by the local IRB and protocol changes will be relayed to NIH. AEs and SAEs occurring during the course of the trial will be collected, documented, and reported in accordance with IRB requirements.

Definition of AE and SAE

Adverse events are defined as any untoward medical occurrence that may present itself during treatment or administration of an intervention, and which may or may not have a causal relationship with the treatment.

Serious adverse events are defined as any medical occurrence that:

- Results in death,
- Is life-threatening,

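### Trait fatigue is collected at weeks 1, 2 and 4, but the Aim 1 model has only two timepoints, so the plan holds no prespecified estimate of whether an effect lasts

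*Combined protocol and SAP*

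**What the plan says.** Study Design and a-tDCS Treatment calls the trial longitudinal and schedules three telephone assessments: "Follow-up assessments of state and trait fatigue will be performed via phone at one (Follow-up 1), two (Follow-up 2), and four weeks post-treatment". The same section fixes the primary comparison: "The primary study outcome will be the comparison of the FSS scores obtain at baseline (Visit 1) and one week post-tDCS (Follow-up 1".

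Statistical Analysis gives one model for Aim 1, with a between-subjects group factor and a "within-subjects factor of TIMEPOINT (pre, post), mixed model ANOVA will be used to test this hypothesis". It does not say which visit counts as post; only the primary-outcome sentence ties it to Follow-up 1. It adds that effect sizes will be calculated to power later studies.

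Biostatistical Justification sets a minimum of 8 per group and enrols 12 per group "to account for any drop-out, loss to follow-up, or complications during data collection". On missing values, DSMP Administration says only that the database will be examined for them; no analysis rule is given. Potential Problems / Solutions leaves the best follow-up period to future studies.

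The FSS is named explicitly for week 1. For weeks 2 and 4 the text says trait fatigue, and Table 1 lists three trait instruments. That the FSS is repeated at those calls is a reasonable inference, not a stated fact. Figure 2 is not available to settle it.

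**The concern.** Two of the three post-treatment assessments of the primary construct have no planned use. Recruitment and Consent describes the FSS as covering the previous seven days, so the week-1 score describes only the first week after stimulation. A later trial drawing on this pilot's effect size will need to know whether that difference is still present at one month when it chooses its endpoint time. Without prespecified contrasts at weeks 2 and 4, any statement about persistence will be post hoc, and in 24 people there is a real risk of selective reporting.

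A second, conditional issue concerns missing data. The plan expects some loss to follow-up but does not say what happens to a participant who misses the week-1 call and is reached at week 2 or 4. A classical two-level ANOVA needs both values and would set that person aside, although later scores on the same construct exist.

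**Working it through.** **1. Visits against planned analyses**

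| Visit | Fatigue measure | Planned Aim 1 use |
|---|---|---|
| Baseline (Visit 1) | FSS | pre |
| Follow-up 1 (week 1) | FSS, explicit | post, by the primary-outcome sentence |
| Follow-up 2 (week 2) | trait fatigue | none stated |
| Follow-up 3 (week 4) | trait fatigue | none stated |

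The post-hoc responder analysis names no visit. Data Management and Analysis promises effect sizes with 95% confidence intervals but does not tie them to weeks 2 or 4.

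**2. The plan's own figures**

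The plan states that "a minimum sample of 8 individuals in each group is required" and enrols 24. The allowance is 24 − 16 = 8, or 8/24 = 33%, which is 4 of 12 per arm. Each participant without a week-1 score costs 1/12 = 8% of an arm in a complete-case analysis. The 8 per group cannot be reproduced, because neither a standard deviation nor a within-person correlation is stated. That is a separate matter, and nothing below rests on it.

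**3. What later visits add to the week-1 contrast**

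Assumptions: equal variance (set to 1), the same correlation r between any two of the four visits, known covariance, baseline entered as a timepoint, 12 per arm, and k per arm missing week 1 only. None of these correlations is in the documents; r is varied from 0.5 to 0.9.

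- Residual variance of a week-1 score given the other three visits: R = (1 − r)(1 + 3r)/(1 + 2r).
- Variance of the week-1 minus baseline mean in one arm: V = 2(1 − r)/12 + R × [1/(12 − k) − 1/12].
- Effective n per arm = 2(1 − r)/V. Complete cases give 12 − k.

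At r = 0.7, R = 0.3 × 3.1/2.4 = 0.3875:

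| k | V | Effective n | Complete cases | Gain | Effective n, r from 0.5 to 0.9 |
|---|---|---|---|---|---|
| 0 | 0.0500 | 12.00 | 12 | 0% | 12.00 |
| 1 | 0.0529 | 11.33 | 11 | 3.0% | 11.32 to 11.35 |
| 2 | 0.0565 | 10.63 | 10 | 6.3% | 10.60 to 10.67 |
| 3 | 0.0608 | 9.87 | 9 | 9.7% | 9.83 to 9.93 |

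So there is no gain with complete data and roughly 3% to 10% with 1 to 3 missed calls per arm. Part of this comes from baseline alone: a likelihood fit to just two timepoints with k = 1 already gives about 11.05 to 11.23.

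**4. The average over follow-ups**

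Per-person variance of a single-week change from baseline is 2(1 − r). For the mean of three follow-ups minus baseline it is (1 + 2r)/3 + 1 − 2r = (4/3)(1 − r). The ratio is (4/3)/2 = 0.67, one third less at any r. This is a different quantity from the primary comparison.

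**5. Why baseline must stay in**

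A week-1 contrast that ignores baseline has per-person variance 1 against 2(1 − r) for the planned change, a ratio of 1/[2(1 − r)]: 1.25, 1.67 and 2.50 at r = 0.6, 0.7 and 0.8. A model with only the three follow-ups and no baseline term would be noisier than the current plan at these correlations.

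**The case against.** A single prespecified primary timepoint is legitimate in a 24-person pilot. Aim 1 hypothesises a reduction after five days of stimulation, not a lasting one, and the plan openly leaves follow-up periods to future work. All of that stands, and the primary test should not change.

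A reader might infer that the trial cannot say whether an effect lasts. The documents do not support that. The week-2 and week-4 scores will exist, and Data Management and Analysis allows post-hoc exploratory analyses with Type I error control and effect sizes with confidence intervals. This is partial cover, since those weeks are not named. What is missing is prespecification, not the ability to look.

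A reader might also infer that anyone missing the week-1 call is dropped. That depends on how the model is fitted, and the documents state no missing-data rule. A classical ANOVA would exclude the person. If mixed model ANOVA means a likelihood fit, the person stays through the baseline score but adds little. Enrolling 24 against a stated minimum of 16 also absorbs some loss, though it supplies neither a rule nor a durability estimate.

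Finally, it is tempting to quote how well weeks 2 and 4 would predict a missing week-1 score: 2r²/(1 + r), or 58% at r = 0.7. That overstates the benefit, because baseline alone already explains r² = 49% and all three visits together explain 61%.

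**Conclusion.** The gap is real but limited. Trait fatigue at weeks 2 and 4 has no planned analysis, so the trial has no prespecified estimate of persistence. The exclusion of participants who miss only week 1 is conditional on a classical ANOVA fit. The precision gain for the primary contrast is modest: nil with complete data, and about 3% to 10% in effective n with 1 to 3 missed calls per arm. These sizes rest on compound symmetry with r between 0.5 and 0.9, an assumption outside the documents. The reason to act is the week-2 and week-4 contrasts, which the plan lacks and could have at almost no cost. This is an improvement that should be made; the primary comparison itself is sound in form.

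**What to change.** In Statistical Analysis:

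- State that post means Follow-up 1 for the FSS, and keep the baseline versus Follow-up 1 group comparison as the single primary test.
- State that the FSS is the trait instrument at all three calls, if that is the intention.
- Estimate the primary contrast from one likelihood-based repeated-measures model with baseline FSS (as a timepoint or a covariate) and Follow-ups 1, 2 and 3, group by week, and a simple covariance structure. Include every participant with any follow-up FSS, and say how those with none are handled.
- Report the group contrasts at weeks 2 and 4, and the average over weeks 1 to 4, with 95% confidence intervals, labelled secondary.

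The cost is protocol wording and one model; no calls, visits or participants are added. The downsides are a slightly more complex model at n = 24, a covariance assumption, and the usual requirement that missed calls be explainable by the observed data. A complete-case two-timepoint analysis can be kept as a sensitivity check.

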Prospective participants will be recruited from our bioinformatics enabled post-stroke recruitment database which is maintained by the NIH Center of Biomedical Research Excellence in Stroke Recovery at the Medical University of South Carolina. This database, RESTORE, contains over 1200 individuals post-stroke who have consented to be contacted for research purposes. Veterans from our VA-approved recruitment data have agreed to have their contact information placed in RESTORE and their veteran-status is highlighted. Prospective participants more than six months post-stroke will be identified by their response to question 4 of the Personal Health Questionnaire Depression Scale (PHQ-8) stored in their database record. A response of 2 or 3 indicates "Feeling tired or having little energy" on at least half the days over the last 2 weeks. Veterans who participated in the recently completed VA RR&D sponsored study "Fatigue and Mobility in Stroke: a Biomechanical and Neurophysiological Investigation" (IK1 RX0003126, CDA-1, PI: [name]) will be preferentially contacted and recruited to participate in this project. Initial contact will be made with prospective participants via telephone. The project basics will be explained and interested individuals will be invited to our research laboratory for final eligibility screening and consent. *Full inclusion and exclusion criteria are listed in the "Protection for Human Subjects" section.* Once consented, participants will complete a set of questionnaires to assess levels of state and trait fatigue, depression, anxiety, and pain. State fatigue is defined as a participant's instantaneous perception of fatigue and is measured on a 0-10 visual analogue scale (f-VAS) with 0 signifying no feelings of fatigue and 10 representing the most fatigued an individuals could imagine. Trait fatigue refers to an individual's perception of fatigability, i.e. how fatigue affects their ability to perform activities of daily living and participate in social and physical activities. The most common instrument used to measure trait fatigue is the Fatigue Severity Scale (FSS, Krupp et al. 1997). The FSS is a nine-question, scored on a 1-7 likert scale, self-reported questionnaire assessing the impact of fatigue on a variety of activites over the last seven days. An average score of 4 on the FSS signifies clinically relevant fatigue (total FSS score ≥ 36). Additional clinical tests and questionnaires will be performed to measure physical disability (gait speed), balance, and quality of life. Women of childbearing potential will perform a urinalysis to determine pregnancy status. Pregnant women will be excluded due to unknown effects of tDCS on fetal development and mother's milk. The

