
[figure not shown]

Figure 2: Research protocol timeline. Three additional followup phone-calls to assess fatigue will be performed 1, 2, and 4 weeks post the participants' last tDCS treatment.

full list of questionnaires and clinical measures is presented in Table 1. *The primary outcome for this study is trait fatigue measured by the FSS.*

Study Design and a-tDCS Treatment

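### The primary FSS change runs from an on-site questionnaire at Visit 1 to a phone assessment at Follow-up 1 with no step to hold the mode constant; the randomised contrast is protected from a shift common to both arms, but the uncontrolled summaries and the precision are not

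*Combined protocol and SAP*

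**What the plan says.** Recruitment and Consent: candidates are "invited to our research laboratory for final eligibility screening and consent", and then "Once consented, participants will complete a set of questionnaires to assess levels of state and trait fatigue". The FSS is described there as a nine-item, 1-to-7 "self-reported questionnaire assessing the impact of fatigue". The section does not say whether the participant fills in the form alone or staff read it out.

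Study Design and a-tDCS Treatment: "Follow-up assessments of state and trait fatigue will be performed via phone" at one, two and four weeks. The primary outcome is the "comparison of the FSS scores obtain at baseline (Visit 1) and one week post-tDCS". No phone script, printed form for the call, check that the two modes agree, or description of the caller is given.

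Statistical Analysis: Aim 1 is tested by a mixed ANOVA with GROUP (active, sham) and TIMEPOINT (pre, post), and effect sizes will be calculated to power later studies. Biostatistical Justification bases the sample size on the within-between interaction. Potential Problems / Solutions adds a post-hoc response analysis, counting individual changes above 0.45, for the same purpose.

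State fatigue is a separate measure that "is measured on a 0-10 visual analogue scale (f-VAS"). It is not primary: "The primary outcome for this study is trait fatigue measured by the FSS".

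**The concern.** People may answer the same fatigue items differently on a form in a laboratory and by voice to a caller. If they do, each participant's primary change score contains a mode effect as well as any change in fatigue.

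Two things are at stake. An average mode shift would bias any summary that is not a contrast with sham. These summaries matter here because the pilot is meant to inform the design of later studies, and the response rate is defined on individual change without reference to sham. Separately, if the mode effect differs from person to person, that variation adds to the SD of FSS change and costs precision in the randomised comparison of 12 against 12.

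State fatigue raises a smaller version of the same point. By phone, a visual scale presumably becomes a spoken number unless the participant has a form in hand, and the plan does not describe the substitution.

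**Working it through.** **Inputs from the documents.** MCID 0.45 FSS points; alpha 0.05; 80% power; minimum 8 per group; 12 per arm enrolled; nine items, averaged.

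**Assumed, because the documents are silent.** SD of FSS change 0.7 to 1.0; mean improvement 0.20 (sham) and 0.65 (active), which differ by the MCID; a mode shift of 0.2 points towards lower phone scores; a person-level mode SD of 0.3 to 0.5, independent of true change; two-sided tests; the post value in the ANOVA is Follow-up 1.

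**The plan's own figure.** No SD or pre-post correlation is stated, so 8 per group cannot be reproduced directly. Solving backwards with the noncentral t on change scores (equivalent to the 2 x 2 interaction), 8 per group for a 0.45 difference implies a change SD of about 0.28 to 0.30. Alternatively, 0.45 read as Cohen's f gives 8 per group at a pre-post correlation of 0.29 to 0.39. The point below does not depend on which was meant.

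**1. The interaction.** Write the mean change in each arm as true change plus mode shift m. The contrast is (active + m) - (sham + m) = active - sham, so m drops out. A simulation with 12 per arm, no treatment effect, change SDs of 0.30, 0.75 and 1.0, and shifts of 0, 0.20 and 0.45 agrees: bias within 0.003 points, type I error 0.049 to 0.051.

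**2. Summaries without a sham contrast.** In the same simulation, with a 0.20 shift and no treatment effect:

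| Change SD | False-positive rate, TIMEPOINT | False-positive rate, within-arm test | Share dropping > 0.45: no shift, then 0.20 shift |
|---|---|---|---|
| 0.30 | 0.88 | 0.56 | 0.07, 0.20 |
| 0.75 | 0.24 | 0.14 | 0.27, 0.37 |
| 1.0 | 0.16 | 0.10 | 0.33, 0.40 |

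**3. Response rate with a treatment effect.** The average of nine items moves in steps of 1/9. Since 4/9 = 0.444 falls short of 0.45, response means a drop of at least 5/9 = 0.556. The normal approximation with the cut midway, at 0.50, is

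response = 1 - Phi((0.50 - mean improvement - shift) / SD).

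| Change SD | Sham: no shift, 0.2 shift | Active: no shift, 0.2 shift | Active minus sham: no shift, 0.2 shift |
|---|---|---|---|
| 0.7 | 33.4%, 44.3% | 58.5%, 69.2% | 25.1, 24.8 points |
| 0.8 | 35.4%, 45.0% | 57.4%, 66.9% | 22.1, 21.9 points |
| 1.0 | 38.2%, 46.0% | 56.0%, 63.7% | 17.8, 17.7 points |

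Each arm moves by about 8 to 11 points; the difference between arms hardly moves.

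**4. Precision.** Inflated SD = sqrt(SD² + mode SD²). The smallest ratio is sqrt(1.0² + 0.3²)/1.0 = 1.044 and the largest is sqrt(0.7² + 0.5²)/0.7 = 0.860/0.7 = 1.229, a rise of 4 to 23%.

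Power by noncentral t for a 0.45 difference, 12 per arm, 22 df, noncentrality 0.45 / (SD x sqrt(2/12)):

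| Change SD | No mode variation | Mode SD 0.3 | Mode SD 0.5 |
|---|---|---|---|
| 0.7 | 32.5% | 28.3% | 23.2% |
| 0.8 | 26.1% | 23.5% | 20.1% |
| 1.0 | 18.4% | 17.3% | 15.7% |

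The loss is about 1 to 9 points. At the much smaller SD of 0.30, near the value implied by 8 per group, power at 12 per arm would fall from 94% to 83% with a mode SD of 0.2, and to 56% with 0.4. The last case assumes a mode SD larger than the SD of change itself.

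**The case against.** The strongest reply is that the analysis carrying Aim 1 is a randomised comparison with sham. Both arms have the same visits and calls, so a common mode shift cannot create a treatment effect. That stands. A reader might infer from the change of mode that the primary test is biased; the documents do not support that. Bias there would need a mode effect that differs by arm. The design is called single-blind without saying whether callers are blinded, so an arm-specific interviewer effect cannot be excluded, but nothing in the plan shows one.

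The size and sign of any shift are also assumed, and the baseline FSS might already be read aloud, since the plan does not say. That stands too: it makes the effect uncertain, but it does not supply a procedure that keeps the two assessments alike. The response analysis is labelled post-hoc and does not test the hypothesis. Its declared use is nevertheless to power future studies, where within-arm rates could be carried forward.

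It is tempting to say that the f-VAS cannot be given by phone, or that phone and on-site ratings cannot be compared. That goes too far. A 0-10 rating can be spoken, a form in hand is not ruled out, and Statistical Analysis specifies no f-VAS analysis.

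Nor do the documents support a claim that ability to respond by phone is ignored. Initial contact and explanation of the study are by phone, and inability to follow three-step instructions is an exclusion. Neither is a formal check on answering a seven-point scale by phone, but together they meet much of the worry.

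**Conclusion.** The point holds as a cheap improvement to measurement, not as a flaw in the randomised test. The primary FSS change crosses modes, and the plan has no step to prevent or check that. The GROUP x TIMEPOINT interaction is unbiased under a shift common to both arms. The TIMEPOINT effect, the within-arm changes and the 0.45-point response rate are not protected, and variation in the mode effect between people would add noise to the primary contrast.

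The sizes are conditional on the assumptions listed in the working, none of which the documents supply. Under them, a shift moves response rates in both arms together, and the loss of power is modest beside how low power already is at change SDs of 0.7 to 1.0. A reader might infer that mode variation alone takes an adequately powered trial below target. At those SDs the documents do not support that, because 12 per arm has only 33% to 18% power for a 0.45 difference before any mode noise is added.

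**What to change.** Use one mode for both halves of the primary comparison. At Visit 1, administer the FSS with the same read-aloud script and printed form that will be used in the follow-up calls. Send the form home so that the participant has it in hand at one, two and four weeks, and write the procedure into the protocol.

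As a secondary step, collect a spoken 0-10 fatigue rating beside the f-VAS at in-person visits, so that the phone ratings of state fatigue have a matching baseline.

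The cost is a script, a printed form and a few more minutes at Visit 1. The design, the sample size and the Aim 1 model do not change.
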